6.3.14.3 Unsolicited Adverse Events

Treatment-emergent adverse events (TEAEs) are defined as those adverse events that either start or worsen on or after the date of first vaccination.

All following TEAEs will be included in the summary tables:

• All AEs occurred on the day of vaccination (vaccination 1, vaccination 2 or vaccination 3) and during the next 27 days [date of vaccination + 27 days]

AND

^{**} Oral temperature; no recent hot or cold beverages or smoking.

^{***} When resting heart rate is between 60 - 100 beats per minute. Use clinical judgement when characterizing bradycardia among some healthy subject populations, for example, conditioned athletes.

Statistical Analysis Plan

• SAEs, medically significant events (i.e., AEs medically attended) or new onset of chronic illnesses through the date of end study

If a subject missed one or two vaccination injections, the AEs for the corresponding vaccination injections will not be included in the summary. For example, one subject missed vaccination 2, the AEs for the day of vaccination 2 and during the next 27 days will be missing and not be included in the summary tables and figures.

Solicited adverse events continuing beyond Day 7 will be coded by MedDRA and combined with the respective unsolicited adverse events.

For AEs included in the summary tables defined above, numbers of AEs will be summarized by System Organ Class (SOC) and Preferred Term, and also by severity/causality to vaccine. The summaries will be presented by vaccination (any vaccination, vaccination 1, vaccination 2 and vaccination 3) and interval of onset as follow:

- Day 1 to Day 28
 where the AEs will include AEs occurred on/after Day 1 (date of vaccination) until earliest date of (Day 28, date of next vaccination-1, end of study)
- Day 29 to end of considered interval
 where the AEs will include SAEs, medically significant events (i.e., AEs medically
 attended) or new onset of chronic illnesses occurred on/after Day 29 to earliest date of
 (date of next vaccination-1, end of study)
- Day 1 to end of considered interval where the AEs will include AEs occurred on/after Day 1 (date of vaccination) until earliest date of (date of next vaccination-1, end of study)

The original verbatim terms used by investigators to identify AEs in the eCRFs will be mapped to preferred terms using the Medical Dictionary for Regulatory Activities (MedDRA) dictionary. The AEs will then be grouped by MedDRA preferred terms into frequency tables according to system organ class. These summaries will be presented by treatment group and overall. When an AE occurs more than once for a subject, the maximal severity and strongest relationship to the treatment group will be counted. Separate summaries will be produced for the following categories:

- AEs
- SAEs
- Unexpected AEs
- AEs that are very likely, probably or possibly related to vaccine

Statistical Analysis Plan

- AEs leading to vaccine withdrawal
- AEs leading to study withdrawal
- AEs medically attended
- New onset of chronic illnesses
- Solicited AEs continuing beyond Day 7

In addition, all TEAEs occurred from the date of first vaccination through the date of end study will be summarized by MedDRA preferred terms into frequency tables according to system organ class for the following categories:

- AEs
- SAEs
- AEs leading to vaccine withdrawal
- AEs leading to study withdrawal
- New onset of chronic illness
- AEs medically attended

The following listings will be produced:

- All pre-vaccination AEs and TEAEs
- AEs leading to vaccine withdrawal
- AEs leading to study withdrawal
- SAEs
- AEs medically attended
- New onset of chronic illnesses
- Solicited AEs continuing beyond Day 7
- Adverse events leading to death

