3.3 Secondary endpoints

- SPR on Study Days, 56 and 168, 4 weeks and 20 weeks after receiving the second Sci-B-Vac[™] vaccination (just prior to receiving the third vaccination), and the SPR on Study Day 196, 4 weeks after receiving the third Engerix-B[®] vaccination
- Number (%) of subjects-reported, solicited (on the day of vaccination and during the next 6 days), unsolicited AE (on the day of vaccination and during the next 27 days), and number of Serious SAEs, medically significant events (condition prompting emergency room visit, physician visit not related to a common disease/not a routine visit or an SAE not related to a common disease) or new onset of chronic illness through Study Day 336. Adverse events will be classified by Medical Dictionary for Regulatory Activities (MedDRA) system organ class and preferred term, severity, seriousness, investigator and Sponsor causality assessment, and time since vaccination.
- Number (%) of subjects with abnormal vital signs, and/or physical examination findings compared to baseline.

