7.1.8 Causality

Relationship of all AE and SAE to the study interventions (causality) should be assessed by the investigator and the sponsor according to the criteria below:

- **Very likely/Certain:** A clinical event with a plausible time relationship to vaccine administration and which cannot be explained by concurrent disease or other drugs or chemicals.
- **Probable:** A clinical event with a reasonable time relationship to vaccine administration; and is unlikely to be attributed to concurrent disease or other drugs or chemicals.
- **Possible:** A clinical event with a reasonable time relationship to vaccine administration, but which could also be explained by concurrent disease or other drugs or chemicals.
- Unlikely: A clinical event whose time relationship to vaccine administration makes a causal
 connection improbable, but which could be plausibly explained by underlying disease or other
 drugs or chemicals.
- **Unrelated:** A clinical event with an incompatible time relationship and which could be explained by underlying disease or other drugs or chemicals.
- **Unclassifiable:** A clinical event with insufficient information to permit assessment and identification of the cause.

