7.2.1 AEs

All new AE or abnormal laboratory test values considered as clinically significant, expected or unexpected related or unrelated experienced after the subject received the study treatment should be recorded in the eCRF. AEs (any untoward medical occurrence in trial subject) do not necessarily have to have a causal relationship with treatment.

As a consistent method of collecting AEs, the subjects will be asked a non-leading question.

The investigator or delegates will record all directly observed AE, and all AE solicited or spontaneously reported by the subject, or reported in the subject's diary.

In addition to solicited AE following vaccination, unsolicited AE will be defined as follows: 1) AE, 2) serious AE (SAE), 3) medically significant event (condition prompting emergency room visit, physician visit not related to a common disease/not a routine visit or an SAE not related to a common disease), 4) investigator-determined new onset of chronic illness (NOCI). Any AE/SAE spontaneously reported at any study visit will be classified accordingly and reported in the eCRF.

AEs will be recorded in terms of medical diagnosis using the Medical Dictionary for Regulatory Activities (MedDRA). When this is not possible, the AE will be documented in terms of signs and symptoms observed by the investigator or as reported by the subject. In this case, each sign or symptom will be coded separately using MedDRA.

In addition, information provided for each AE will include: start date, treatment required if any assessment of the outcome at the time of reporting, causality, severity, and seriousness.

For each symptom the subject experiences, the subject will be asked if the subject received medical attention defined as hospitalization, or an otherwise unscheduled visit to or from medical personnel for any reason, including emergency room visits. This information will be recorded in the eCRF.

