7.7 Unblinding

Unblinding procedure (which incorporates ICH E2A guidance, EU Regulations on clinical trials on medicinal products for human use and US Federal Regulations) is to unblind the report of any SAE that is unexpected and attributable/suspected to be attributable to the investigational product/product, prior to regulatory reporting. Causality will be determined by the investigator.

The IRB/REB will receive blinded or unblinded safety reports in keeping with local requirements. Suspected unexpected serious adverse reactions (SUSAR) reports will be distributed to the investigator and IRB/REB in compliance with local regulations.

The Medical Monitor will be responsible for the unblinding of events that meet the study stopping rules, if this is determined to be necessary for evaluation purposes by the data monitoring committee.

The blind should ordinarily be broken for regulatory submission.

Unblinding in case of an emergency is described below. However, it should be noted that is not anticipated that such occurrence will be encountered in the conduct of the study since it is unlikely that the knowledge of the vaccine received by the subject will affect his/her medical management.

The investigator may unblind a subject's treatment assignment **only in the case of an emergency**, when knowledge of the study treatment is essential for the appropriate clinical management or welfare of the subject. The unblinding should be formally completed in IWRS. Whenever possible, the investigator must first discuss options with the Study Medical Monitor or appropriate VBI study personnel **before** unblinding the subject's treatment assignment in IWRS. If this is impractical, the investigator must notify the Contract Research Organization (CRO) and sponsor as soon as possible, but without revealing the treatment assignment of the unblinded subject, unless that information is important for the safety of subjects currently in the study. The date and reason for the unblinding must be recorded in the appropriate data collection tool. If the Investigator does not have access to IWRS or is having technical issues, the

investigator can contact unblinded staff at the site for the treatment but this must be clearly documented in the source notes and should only be used as a back-up option.

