- **Emergence during vaccination phase**: start date on or after the first date of injection of study vaccine or, adverse event increase in severity including to "serious" adverse event.

If an adverse event start date is equal to the first date of vaccination injection, missing or unknown, the adverse event will be considered as emergent.

When start and/or end dates of an adverse event are only partially known, adverse events will be categorized as emergent before, during (or after) vaccination phase using the following rules:

• If the partial end date is before (<) the first study vaccination (i.e., year or year & month is/are before the first study vaccination year or year & month) then the adverse event is emergent before vaccination phase.

Statistical Analysis Plan

If the partial start date is equal or after (≥) the first study vaccination (i.e., year or year & month is/are after or the same as the first study injection year or year & month) then the adverse event is emergent during vaccination phase.

The **maximum event severity** is the greatest severity associated with a preferred term for a reported adverse event according to the following order: Mild < Moderate < Severe < Potentially life threatening. Unknown/ Missing severity is considered as potentially life threatening.

Multiple AEs with the same PT for the same subject are counted only once.

Vaccination-related Adverse Events are those for which the cause has been evaluated by the investigator, and recorded either as very likely/certain, possibly related, probably related or unknown/missing.

Pre-Study, Concomitant and Post-Study Medications

A **pre-study medication** is a medication used only before the first study vaccination (i.e. medication end date < first study vaccination date).

A **post-study medication** is a medication used only after study termination (i.e. medication start date > study termination date). This will not be collected in the clinical database and will not be reported in the CSR.

All other medications are **concomitant**.

When start and/or end dates of a medication intake are missing, the medication is considered as concomitant with the study vaccination schedule.

If the first study vaccination date is missing then the medication is considered as concomitant with the study vaccination schedule, provided that the study vaccine was administered to the subject.

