6.3.14.6 Physical Examination

The results of the physical examination will be listed by subject and time-point. Any clinically significant difference in physical examination from previous visit will be summarized by visit.

Statistical Analysis Plan

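### Three SAP safety outputs do not match the protocol's secondary safety endpoints: medically significant events, physical examination against baseline, and sponsor causality

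*SAP*

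**What the plan says.** **Medically significant events.** Protocol 3.3 covers a condition that leads to an emergency room visit, or a "physician visit not related to a common disease/not a routine visit or an SAE not related to a common disease". Section 7.2.1 repeats this definition. It also records, as a separate item for each symptom, whether medical attention was received, meaning hospitalisation or an "unscheduled visit to or from medical personnel for any reason, including emergency room visits". SAP 6.3.14.3 decides which treatment-emergent events enter the summaries. Beyond the 28-day windows it admits "SAEs, medically significant events (i.e., AEs medically attended) or new onset of chronic illnesses through the date of end study". It repeats the same equation in the interval from Day 29 onward. Its tables and listings include medically attended events, but none is for medically significant events.

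**Physical examination.** The Protocol 3.3 endpoint is "Number (%) of subjects with abnormal vital signs, and/or physical examination findings compared to baseline". SAP 6.3.14.6 says: "Any clinically significant difference in physical examination from previous visit will be summarized by visit". Vital signs, the other half of that endpoint, are compared with baseline in SAP 6.3.14.5.

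**Causality.** Protocol 3.3 classifies adverse events by the assessments of both investigator and sponsor. Under 7.1.8 the relationship of every event "should be assessed by the investigator and the sponsor according to the criteria below". SAP 6.1.1 states that vaccination-related "Adverse Events are those for which the cause has been evaluated by the investigator". SAP 6.3.14.3 tabulates causality without naming an assessor, and no output shows the sponsor's view. Protocol 7.7, on unblinding, says: "Causality will be determined by the investigator".

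**The concern.** Comparing safety and reactogenicity is a stated secondary objective, and the trial is meant to support licensure. The SAP says it is based on protocol version 2.0 and gives no reason for any of the three departures. The report would then present three descriptive quantities as protocol endpoints although the protocol did not define them.

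- Visits for common illness would be counted as medically significant.
- An examination finding that persists would appear in the by-visit summary only when it first arises.
- A disagreement between investigator and sponsor on relatedness would not be visible in any output.

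**Working it through.** There is no planned figure to reproduce, so the check sets the texts side by side.

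**1. Medically significant events**

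- Take an unscheduled doctor's visit for a cold between V3 and V4. Under Protocol 7.2.1 this is medical attention. Under 3.3 it is not a medically significant event, because it concerns a common disease. Under SAP 6.3.14.3 it enters the tables as one.
- How much follow-up does the rule govern? On the nominal schedule, all adverse events are included for 28 days from each vaccination: Days 0–27, 28–55 and 168–195, or 3 × 28 = 84 days. The rule decides entry on Days 56–167 (112 days) and 196–336 (141 days). That is 253 of the 337 days from Day 0 to Day 336.
- The SAP also plans tables of all treatment-emergent events from first vaccination to study end. Those do not isolate the endpoint category either.
- Are the data there? Yes. Protocol 7.2.1 requires events to be classified into these categories in the eCRF, and 7.2.4 requires medically significant events to be documented there.

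**2. Physical examination**

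The schedule has examinations at screening, V1 and each of V2 to V6. SAP 6.3.1 sets baseline as the last pre-vaccination measurement. Two example subjects, both normal at baseline:

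| Course of finding | Visits counted against baseline | Visits counted against previous visit |
|---|---|---|
| Appears at V2, persists to V6 | V2, V3, V4, V5, V6 (5) | V2 (1) |
| Appears at V2, gone at V6 | V2, V3, V4, V5 (4) | V2, and possibly V6, since the wording gives no direction |

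The general baseline rule in SAP 6.3.1 does not repair this, because 6.3.14.6 specifically names the previous visit. Protocol 6.1.5 adds a difficulty. Only the screening or Day 0 examination has to be full, and later ones may be directed by history. The previous visit may therefore not have examined the same body system.

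**3. Causality**

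| Investigator | Sponsor | Related under SAP 6.1.1 | Disagreement visible in any SAP output |
|---|---|---|---|
| Related | Related | Yes | None to show |
| Related | Not related | Yes | No |
| Not related | Related | No | No |
| Not related | Not related | No | None to show |

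The SAP counts unknown or missing causality as related. That is cautious, but it deals with absent assessments and not with disagreement. Protocol 7.1.8 requires both assessments, so the sponsor's view should be available to tabulate.

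**The case against.** Several points on the other side have force.

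- **The protocol's own collection wording is loose.** The schedule of events limits unsolicited events at V3 and V6 to those needing medical attention. Section 6.3.7 collects on that basis at the last visit, and 6.1.10 asks about doctor or emergency room visits up to Day 336. This may explain the SAP's wording. It concerns collection, however, and does not redefine the endpoint in 3.3.
- **The substitution adds events and does not hide them.** Tables are by system organ class and preferred term, with serious events and new chronic illness shown separately, so common illnesses can be recognised by term. This stands as mitigation, but the endpoint category itself is still not tabulated.
- **Examination data are not lost.** Results are listed by subject and time point, and a new or worsened finding can also qualify as an adverse event under Protocol 7.1.1. This stands. The fault is confined to the summary.
- **Section 9 of the protocol allows changes to non-confirmatory analyses if the clinical study report explains them.** That is a route for documenting a deliberate change. The SAP does not present these as changes.

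Three stronger readings are tempting, and the documents do not support them.

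- *A reaction suspected only by the sponsor would escape expedited reporting.* Protocol 7.7 concerns unblinding. Under 7.3.1 the medical monitor or pharmacovigilance agent assesses each serious report, and 7.4 makes the sponsor responsible for reporting suspected reactions. The definition in 7.1.10 is not limited to the investigator's opinion. Section 7.7 itself lets the medical monitor break the blind case by case.
- *Common-illness visits cost the safety comparison a calculable amount of power.* Protocol 9.8 has no safety hypotheses, and neither document gives event rates. Any test statistic would rest on invented inputs and describe a test that is not planned.
- *An event must count as related if either assessor says so.* Protocol 3.3 asks for classification by both assessors but sets no such combining rule.

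**Conclusion.** All three mismatches are in the current text, and the SAP as written would not deliver these parts of the secondary safety endpoints. The fault lies in definition and reporting. The co-primary analyses, type I error and power are untouched, the vital-signs half of the endpoint is correct, and the underlying records are kept. The size of any distortion cannot be estimated from the documents.

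Two readings underlie this conclusion. First, the slash in Protocol 3.3 is taken to exclude a physician visit that is either for a common disease or routine. If a visit needed only to be non-routine to qualify, the common-disease wording would do nothing for unscheduled visits. Second, the investigator-only reading of relatedness rests on SAP 6.1.1 together with the absence of any sponsor output, because 6.3.14.3 names no assessor.

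Separately, the sentence in Protocol 7.7 giving causality to the investigator conflicts with the joint assessment in 7.1.8 and sits uneasily with 7.4.

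**What to change.** Before database lock:

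1. **SAP 6.3.14.3.** Delete the parenthesis that equates the two categories, in both places. Tabulate and list medically significant events from the classification in Protocol 3.3 and 7.2.1. Keep medically attended events as their own table.
2. **SAP 6.3.14.6.** Summarise by visit the number and percentage of subjects with a clinically significant finding that is new or worse than baseline. Add a note that examinations after baseline may be history-directed, so an absent finding may mean that the system was not examined.
3. **SAP 6.1.1 and 6.3.14.3.** Add a tabulation of related events by sponsor causality beside the investigator's, and name the assessor in each table.
4. **Protocol 7.7.** Reconcile the causality sentence with 7.1.8 and 7.4.

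If any of the three SAP definitions was intended, the alternative is to state it as a departure from the protocol and give the reason.

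The cost is SAP wording, a few table shells and one protocol clarification. The protocol already calls for the data items, so no new collection should be needed. It is worth confirming that the eCRF holds the medically significant event classification and the sponsor's causality field as specified.

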6.3.14.4 Clinical Safety Laboratory Tests (hematology, biochemistry and urinalysis)

Laboratory values (hematology, biochemistry and urinalysis) will be listed by subject and study time point including changes from baseline (with the exception of urinalysis). The baseline for the laboratory values will be the latest non-missing result obtained before first vaccine injection.

All laboratory (e.g., hematology, chemistry) data will be summarized using descriptive statistics. Summaries will be provided for the observed values and changes from baseline at each scheduled visit.

Statistical Analysis Plan

The changes in biochemistry/hematology from baseline will only be calculated in the clinical laboratory sub-study analysis set (SSA 1). In addition, absolute and change from baseline values will be categorized according to the toxicity scales (See protocol Appendix 4 for laboratory parameters) and summarized by time point using shift tables.

6.3.14.5 Vital Signs

Vital signs data will be listed by subject including changes from baseline. The baseline for the vital signs measurements will be the latest non-missing results obtained before first vaccine injection.

All vital sign data will be summarized using descriptive statistics. Summaries will be provided for the observed values and changes from baseline at each scheduled visit. In addition, absolute and change from baseline values will be categorized according to the toxicity scales (See protocol Appendix 3 for vital signs) and summarized by time point using shift tables.

